**(6) Evaluation Indicators:**

**Key research indicators**

In this study, the performance of the prediction model was comprehensively evaluated by the following five types of indicators, and all indicators reported point estimates and 95% confidence intervals (1000 times repeated sampling by the Bootstrap method): 1) discrimination: the C-index (Concordance Index) was used to evaluate the consistency of the model's ranking of individual survival time (two patients were randomly selected to predict the probability that the one with longer survival time would actually survive longer); 2) Time-dependent AUC (time-dependent AUC) was used to evaluate the model's ability to distinguish whether an event occurred or not at a preset time point; 3) calibration, the difference between the predicted probability and the actual outcome and the probability distribution were visualized by calibration plot and density plot, and the mean square error of the Brier Score was calculated. 4) Decision Curve Analysis (DCA) was used to evaluate clinical practicability; 5) The proportion of variation explained by the Nagelkerke R^2 assessment model was used.

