## Research content

### 1. Research Objectives

**Main objectives:** 1) To construct a generative image model based on preoperative CT/MRI; 2) the treatment response was evaluated in the training cohort based on the virtual image images generated by the model, including: disease control rate (DCR) and objective response rate (ORR), and compared with the best treatment response images after real treatment; 3) predict the prognosis of patients based on real pre-treatment imaging images (CT/MRI/DSA) and virtual post-treatment images, including progression-free survival (PFS) and overall survival (OS);

**Secondary objectives:** 1) Integrate text information such as patient demographic data, laboratory examination data, and image reports/surgical records to achieve cross-modal fusion and further improve the performance of the model; 2) Adopt machine learning methods based on causal inference to realize the recommendation of diagnosis and treatment plans.

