#### (2) Selection of research subjects:

This project is a real-world study, including retrospective training, validation and testing cohorts and prospective testing cohorts, all registries are derived from real cases in clinical practice, and the collected case data should include the following requirements:

1. Unresectable hepatocellular carcinoma confirmed by histopathological diagnosis and/or clinical diagnosis (typical imaging features, clinical manifestations, laboratory tests, etc.) (Annex: Guidelines for the diagnosis and treatment of primary liver cancer (2024 edition));
2. Patients who receive TACE combined with targeted immunotherapy on the basis of the diagnosis of unresectable hepatocellular carcinoma;
3. Liver function grade Child-Pugh A or B;
4. Over 18 years old, regardless of gender;
5. Expected survival time  $\geq$  3 months;
6. ECOG PS score  $\leq 2$ ;

7. Meet the following laboratory examination parameters;

- 1) Hematologic function: absolute neutrophil count  $\geq 1.0 \times 10^9 / \text{L}$ ; Platelet count  $\geq 50 \times 10^9 / \text{L}$ ; hemoglobin  $\geq 90 \text{ g/L}$ ; The international normalized ratio is less than 1.7 or the prothrombin time is prolonged by no more than 4 seconds,
- 2) Liver function: alanine aminotransferase/aspartate aminotransferase does not exceed 5 times the upper limit of normal; total bilirubin  $\leq 210 \text{ micromol/L} [\leq 2.38 \text{ mg/dL}]$ ; Albumin  $\geq 28 \text{ g/L}$ ,
- 3) Renal function: serum creatinine does not exceed 1.5 times the upper limit of normal.

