## 2) Validity:

Overall survival (OS) is defined as the time from the start of chemotherapy combined with immunotherapy to the patient's death from any cause, measured in "months". For subjects who were still alive at the time of data analysis, OS was calculated based on the date on which the subjects were last known to be alive;

Progression-free survival (PFS): defined as the time from the start of chemotherapy combined with immunotherapy to the first disease progression or death from any cause.

To assess response to treatment in patients with intrahepatic lesions:

- a. Objective response rate (ORR): according to RECIST 1.1 criteria, objective response rate = (CR + PR / CR + PR + SD+PD); Participants with CR + PR efficacy should be retested 4 weeks after the first evaluation.
- b. Disease control rate (DCR): according to RECIST 1.1 criteria, lesion control rate = (CR + PR + SD/ CR + PR + SD + PD); Subjects with CR + PR + SD efficacy should be retested 4 weeks after the first evaluation.

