### **3. Research Methodology**

This study is based on a multicenter retrospective cohort including a prospective test cohort to include patients with unresectable hepatocellular carcinoma who have received TACE in combination with target-immune therapy. The data comes from the clinical diagnosis and treatment records of 8 tertiary hospitals from 2016 to 2025, and strictly follows the preset inclusion standards.

Generative model construction: diffusion model-based treatment response simulator: input data: enhanced CT/MRI images at the patient's baseline, real post-treatment enhanced CT/MRI images and clinical features (Child-Pugh score, AFP level, treatment plan, etc.). Model architecture: The conditional diffusion model was used to dynamically simulate the virtual follow-up images of the best response after treatment with the treatment protocol (TACE embolic agent dose + target immune drug combination) as the generation conditions. Training mechanism: The model is optimized by comparing the differences in deep visual features between the generated images and the real follow-up images to ensure that the generated results conform to the laws of biological evolution. Quantitatively evaluate the visual fidelity of the generated images (FID index <25); The clinical rationality was scored by 3 interventional radiology experts by blind (on a 5-point scale  $\geq$  4 points were considered qualified).

Dynamic survival prediction framework: Capture 256-dimensional semantic feature vectors from the generated virtual images to characterize the dynamic changes of tumor microenvironment. The depth features extracted by the generative model are fused with the patient's clinical variables, and the key predictors are automatically identified through the gated attention mechanism. Survival risk modeling: Construct a Transformer-based time-series survival model to output individualized survival curves and survival probability predictions at key time points (12/24/36 months).

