## **5. The innovation of the project**

This study is a multicenter, retrospective, real-world study of unresectable hepatocellular carcinoma (HCC) undergoing TACE in combination with targeted immunotherapy in the project from January 2016 to June 2025. Baseline imaging data, previous treatments, adverse reactions, clinical outcomes, follow-up imaging data, longitudinal laboratory examination data, etc., were collected to construct a generative model and generate imaging images of the best efficacy after virtual treatment. Combine virtual and real pre-treatment images with other clinical information for accurate prognosis prediction.

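### Nagelkerke R² is a key indicator of explained variation, but for censored OS and PFS it falls as censoring rises, so it cannot be compared across cohorts with unequal follow-up

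*Protocol*

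**What the plan says.** Under Key research indicators (section (6), Evaluation Indicators), the protocol says that model performance will be "comprehensively evaluated by the following five types of indicators", each with a point estimate and a bootstrap 95% interval. The fifth is "The proportion of variation explained by the Nagelkerke" R². No outcome is named for this item, and no version adapted to censoring. The first item of the same list concerns survival, since the C-index is to "evaluate the consistency of the model's ranking of individual survival time".

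The main objectives (section 1, Research Objectives) include prediction of PFS and OS. Section 3, Research Methodology, plans to "Construct a Transformer-based time-series survival model to output individualized survival curves", with survival probabilities at 12, 24 and 36 months. OS is right-censored: for patients alive at analysis, "OS was calculated based on the date on which the subjects were last known to be alive" (Validity).

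The data comprise "retrospective training, validation and testing cohorts and prospective testing cohorts" (section (2), Selection of research subjects). Retrospective cases run "from January 2016 to June 2025" (section 5). Section 6 schedules data collection to the end of 2025 and model evaluation for January to June 2026. Section 3 names the C-index for OS as the main survival measure.

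**The concern.** Nagelkerke R² rescales the model's likelihood-ratio statistic per patient. This works as intended for a binary outcome known for everyone. With censored survival, the likelihood ratio accumulates only as events occur, while every patient stays in the divisor. A cohort observed for a shorter time has fewer events and so a lower R², even if the model predicts equally well in it.

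The protocol gives the measure a fixed meaning, the share of variation explained, and reports it as a key indicator in a project with several cohorts. A reader who sets the retrospective and prospective values side by side could take a drop caused by short follow-up for poor generalisation.

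**Working it through.** The protocol gives no R², sample size, event count or censoring rate, so there is no planned figure to reproduce. The check is whether the measure stays put when only follow-up changes.

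**Inputs from the protocol.** Retrospective entry from January 2016 to June 2025 spans 114 months. Model evaluation is due January to June 2026.

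**Assumptions.**
- Exponential survival, one standard-normal risk score and 500 patients.
- Log-hazard ratio per SD of 1.0, varied over 0.6 and 1.4. Median OS of 15 to 30 months at the mean score.
- Retrospective-like follow-up is uniform over 6 to 120 months (114 months of entry, lock in December 2025).
- Prospective-like follow-up is 6 to 18 months (12 months of entry, lock at month 18). A tighter case is 3 to 12 months, since entry starting about mid-2025 would leave at most about 12 months.

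**Formula.** With l0 and l1 the null and model Cox log partial likelihoods, n the number of patients and LR = 2(l1 − l0):

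R² = [1 − exp(−LR/n)] / [1 − exp(2·l0/n)]

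**Results, median OS 20 months, log-hazard ratio 1.0 (60 replicates).** LR per patient is −ln(1 − numerator). LR per event is −ln(1 − R² with events as divisor).

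| Follow-up (months) | Event share | Numerator | Denominator | R² | LR per patient | LR per event | Harrell's C |
|---|---|---|---|---|---|---|---|
| no censoring | 1.00 | 0.461 | 1.000 | 0.461 | 0.618 | 0.618 | 0.719 |
| 6–120 | 0.74 | 0.396 | 1.000 | 0.396 | 0.504 | 0.681 | 0.736 |
| 12–24 | 0.50 | 0.312 | 0.997 | 0.313 | 0.374 | 0.755 | 0.739 |
| 6–18 | 0.39 | 0.262 | 0.989 | 0.265 | 0.304 | 0.781 | 0.735 |
| 3–12 | 0.28 | 0.204 | 0.960 | 0.212 | 0.228 | 0.812 | 0.747 |

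From 6–120 to 6–18 months the event share is multiplied by 0.39/0.74 = 0.53 and LR per event by 0.781/0.681 = 1.15. The product, 0.60, matches LR per patient (0.304/0.504 = 0.60). So R² falls because there are fewer events per patient, while each event carries slightly more information. The denominator stays near 1 and does not compensate.

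**Other medians, log-hazard ratio 1.0, 6–120 versus 6–18 months.**
- Median 15: 0.409 to 0.301, a fall of 1 − 0.301/0.409 = 26%.
- Median 20: 0.396 to 0.265, 33%.
- Median 30: 0.363 to 0.215, 41%.

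A separate run with 120 replicates gave 0.39, 0.38 and 0.36 against 0.28, 0.24 and 0.22 at medians of 18, 24 and 30 months.

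**Other effect sizes.** Over all nine combinations of three medians (15, 20, 30) and three effect sizes, going from 6–120 to 3–12 months lowered R² by 28% (0.547 to 0.393) to 62% (0.186 to 0.070). Harrell's C changed by −0.002 to +0.022. Fixing the coefficient at its true value moved R² by about 0.003 or less, so the fall is not a fitting artefact.

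**Dividing by events instead.** In the table's setting, that version rises from 0.46 without censoring to 0.56 at 3–12 months. It removes the fall but is not stable either.

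**The case against.** The strongest objection is that the decisions in this project do not rest on R². The planned comparison in section 3 is between three models: clinical variables alone, with real follow-up images, and with virtual images. Fitted to the same patients, they share n and the null likelihood, so R² only re-expresses the model likelihood and censoring cannot reverse their order. The main measure is the C-index, R² is absent from section 3's list of survival measures, and no R² threshold or cross-cohort R² contrast is planned. All of this stands. It limits the point to the meaning of one key indicator and its comparability across cohorts.

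Item 5 names no outcome, and ORR and DCR are among the main objectives. For those, if fully observed, the censoring objection does not apply. The survival reading is the likelier one, because the first two items of the list concern survival, but it is an inference. The Transformer model also has no stated likelihood, and computational detail can sit in an analysis plan. What the protocol itself fixes, however, is the measure and its interpretation as explained variation.

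Three stronger readings are tempting, and the protocol does not support them:

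- *That the prospective cohort is stated to have shorter follow-up.* Its start date and follow-up length are not given. Shorter follow-up is inferred from entry to June 2025 and evaluation in early 2026.
- *That a gap in R² between OS and PFS would be due to follow-up length alone.* Within a cohort both share the same patients and observation window. Their event shares differ mainly because progression also counts as an event, and they are different prediction targets.
- *That the alternative of scoring event status at 12, 24 or 36 months must be biased.* Dropping censored patients or counting them as alive would bias it, but the protocol proposes neither. Inverse-probability-of-censoring weighting avoids the problem. So does restriction to patients who entered at least one full horizon before data lock, provided entry date is unrelated to survival.

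**Conclusion.** The point holds for OS and PFS. A Nagelkerke R² from a Cox-type likelihood per patient depends on the censoring share, so it should not be read as the proportion of variation explained or compared between cohorts with unequal follow-up. With log-hazard SD 1.0 and median OS of 18 to 30 months, an unchanged model scores about 0.36 to 0.40 under 6–120 months of follow-up and about 0.22 to 0.28 under 6–18 months.

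In the settings examined, the fall appeared at every median and effect size. Its size rests on the assumed effect, median and follow-up windows, none of which the protocol gives. One of five key indicator types is affected. The within-cohort ranking of models and the conclusion based on the C-index are not. The item should be corrected, but it does not threaten the main result.

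**What to change.** In item 5 of Key research indicators, name the outcome. For OS and PFS, replace Nagelkerke R² with the scaled Brier score:

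1 − (inverse-probability-of-censoring-weighted Brier score of the model) / (the same score for the Kaplan–Meier null model)

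Report it at those of 12, 24 and 36 months that each cohort's follow-up supports, keep the planned 1000-sample bootstrap interval, and compare cohorts only at horizons that both support. Nagelkerke R² may stay for fully observed binary outcomes such as ORR and DCR.

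The cost is one line of wording, since the Brier score is already planned. The drawback is that later horizons may not be reportable in a cohort with short follow-up: with at most 18 months, only the 12-month value would be available. The weighting also requires a stated model for censoring.

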**Secondary Research Indicators**

1) Safety: the incidence of adverse reactions and the severity of adverse events. Adverse events were

graded using the National Cancer Institute (NCI) Common Adverse Event Evaluation Criteria (CTCAE) version 5.0, which were classified as 1 to 5 based on the severity of adverse events (AEs):

Grade 1: mild; asymptomatic or mild; Seen clinically or diagnostically only; No treatment is required.

Grade 2: moderate; Requires minor, topical, or non-invasive treatments; Age-appropriate instrumental limitations in activities of daily living (e.g., cooking, buying clothes, using the phone, managing money, etc.).

Grade 3: Severe or medically significant but not immediately life-threatening; resulting in hospitalization or prolongation of hospitalization; Disability; Limitation of self-directed activities of daily living (e.g., bathing, dressing, undressing, eating, washing, taking medication, etc., and not being bedridden).

Grade 4: life-threatening; Urgent treatment is required.

Grade 5: AE-related deaths.

## 2) Validity:

Overall survival (OS) is defined as the time from the start of chemotherapy combined with immunotherapy to the patient's death from any cause, measured in "months". For subjects who were still alive at the time of data analysis, OS was calculated based on the date on which the subjects were last known to be alive;

Progression-free survival (PFS): defined as the time from the start of chemotherapy combined with immunotherapy to the first disease progression or death from any cause.

To assess response to treatment in patients with intrahepatic lesions:

- a. Objective response rate (ORR): according to RECIST 1.1 criteria, objective response rate = (CR + PR / CR + PR + SD+PD); Participants with CR + PR efficacy should be retested 4 weeks after the first evaluation.
- b. Disease control rate (DCR): according to RECIST 1.1 criteria, lesion control rate = (CR + PR + SD/ CR + PR + SD + PD); Subjects with CR + PR + SD efficacy should be retested 4 weeks after the first evaluation.

## (7) Intervention methods:

The basic information of patients and related information of treatment plans are collected through the electronic medical record system, including treatment plan, dosing cycle, dosing date, dosage, frequency,

number of cycles, efficacy, adverse reactions, etc. Ensure that the data collected in the study can be traced back to the original medical records.

### **3. Research Methodology**

This study is based on a multicenter retrospective cohort including a prospective test cohort to include patients with unresectable hepatocellular carcinoma who have received TACE in combination with target-immune therapy. The data comes from the clinical diagnosis and treatment records of 8 tertiary hospitals from 2016 to 2025, and strictly follows the preset inclusion standards.

Generative model construction: diffusion model-based treatment response simulator: input data: enhanced CT/MRI images at the patient's baseline, real post-treatment enhanced CT/MRI images and clinical features (Child-Pugh score, AFP level, treatment plan, etc.). Model architecture: The conditional diffusion model was used to dynamically simulate the virtual follow-up images of the best response after treatment with the treatment protocol (TACE embolic agent dose + target immune drug combination) as the generation conditions. Training mechanism: The model is optimized by comparing the differences in deep visual features between the generated images and the real follow-up images to ensure that the generated results conform to the laws of biological evolution. Quantitatively evaluate the visual fidelity of the generated images (FID index <25); The clinical rationality was scored by 3 interventional radiology experts by blind (on a 5-point scale  $\geq$  4 points were considered qualified).

Dynamic survival prediction framework: Capture 256-dimensional semantic feature vectors from the generated virtual images to characterize the dynamic changes of tumor microenvironment. The depth features extracted by the generative model are fused with the patient's clinical variables, and the key predictors are automatically identified through the gated attention mechanism. Survival risk modeling: Construct a Transformer-based time-series survival model to output individualized survival curves and survival probability predictions at key time points (12/24/36 months).

Treatment decision support systems: causal effects deduction: quantifying the expected survival benefit of different treatment regimens (eg, TACE + lenvatinib + pembrolizumab versus TACE + bevacizumab + atezolizumab) using a counterfactual analysis framework. Generate a heat map of treatment regimen comparisons to visualize simulated tumor regression differences. Decision rule: When the median survival benefit of a regimen is expected to be more than 3 months and the confidence probability is greater than 80%, the system preferentially recommends the regimen.

Model validation strategy: Stratified by study center, randomly assigned to the training set (70%), validation set (30%), and multiple test sets.

Survival prediction assessment: main indicators: C-index evaluation of overall survival prediction

accuracy; Secondary indicators: 12/24/36 months of time dependence on AUC to assess discriminant ability at a specific time point; Calibration analysis: The Brier score quantifies the prediction error, and the calibration curve evaluates the risk prediction consistency. Comparative experimental design: baseline model (clinical variables only); benchmark model + real follow-up images; Datum model + generate model virtual image.

Reproducibility & Ethics: The model code and preprocessing process are published in the public repository (GitHub). The self-service resampling method (1000 times) was used to calculate the 95% confidence interval.

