## **2. The entry point and significance of this study**

The entry point of this study is to propose "generative longitudinal prediction": only pre-treatment images are needed to generate high-fidelity post-treatment image predictions, which effectively avoids the clinical dilemma of obtaining real longitudinal follow-up data. This paradigm shift not only solves the problem of longitudinal data scarcity, but also develops a new approach to treatment simulation based on digital twins. Clinicians can intuitively evaluate the possible efficacy of different regimens through the virtual multi-time point images generated by the model before treatment, providing a visual basis for individualized treatment decisions. This study integrates generative AI and dynamic risk models to achieve: 1. From static assessment to dynamic deduction; 2. Survival prediction is moved forward; 3. Individualized optimization of treatment plan. It is expected that we can provide more accurate and individualized treatment decision support for patients with advanced liver cancer without relying on longitudinal data, and ultimately improve the survival prognosis and quality of life.

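### The model is meant to predict before treatment, but the protocol sets no input cut-off and does not say whether embolic dose is planned or delivered, so post-time-zero information can enter and a gain cannot be credited to the virtual image

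*Protocol*

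**What the plan says.** Section 2 (The entry point and significance of this study) states that "only pre-treatment images are needed to generate high-fidelity post-treatment image predictions". Clinicians are to compare regimens using "virtual multi-time point images generated by the model before treatment".

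The inputs are spread over several sections:

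- **Generator, images.** Main objective 1 is "To construct a generative image model based on preoperative CT/MRI". Section 3 (Research Methodology) likewise names enhanced CT/MRI at baseline, with real post-treatment images used in training.
- **Generator, conditions.** Section 3 generates the virtual image "with the treatment protocol (TACE embolic agent dose + target immune drug combination) as the generation conditions". It also lists the treatment plan among the clinical features.
- **Source of treatment data.** Section (7), Intervention methods, takes these from the electronic medical record, "including treatment plan, dosing cycle, dosing date, dosage, frequency", together with the number of cycles.
- **Prognosis model.** Main objective 3 is to "predict the prognosis of patients based on real pre-treatment imaging images (CT/MRI/DSA) and virtual post-treatment images".
- **Multimodal extension.** Secondary objective 1 adds text that includes "image reports/surgical records".
- **Comparison.** Section 3 sets up three models. The first is the "baseline model (clinical variables only"; the other two add real follow-up images or virtual images. The main survival measure is the C-index for overall survival.

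Overall survival runs from the start of therapy. No section gives a date after which data may not be used as a predictor.

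**The concern.** A prognostic model is only as useful as its inputs are available at the moment of prediction. Here that moment is before treatment. An amount of embolic agent taken from a chart is, on the natural reading, what was given. A total over sessions also depends on the patient living long enough to have the later sessions. A procedure record has the same timing problem, as does an angiogram if it was taken in the TACE session.

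Two things are at stake. First, the C-index from recorded values may not describe performance at the point of decision. Second, the contrast that tests the project's central idea (clinical variables against clinical variables plus virtual image) mixes the contribution of the image with that of the treatment information used to generate it.

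**Working it through.** The protocol gives no figure to reproduce, so the main check sets each input against the stated moment of use.

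1. **Embolic agent dose** (generator condition, section 3). A planned or hypothetical amount can be entered before treatment. A delivered amount is known only once the session is done, and a cumulative amount only after the last session. The protocol does not say which is meant, and its only stated source is the record of care.
2. **DSA** (prognosis model, main objective 3). It is labelled pre-treatment but given no timing. If it is the angiogram of the TACE session, which is an assumption, it does not exist when the regimen is chosen.
3. **Surgical records** (secondary objective 1). Without a cut-off date these can include the record of the TACE procedure itself.
4. **Other data.** Section 5 lists adverse reactions and longitudinal laboratory data among what is collected to construct the generative model. The lack of a time limit is therefore general.
5. **Comparator.** Drug combination and embolic dose reach the virtual-image model through generation. Whether the clinical-only model holds them depends on what counts as a clinical variable, which section 3 does not define. Treatment plan is named as a clinical feature; embolic dose is named only as a generation condition.

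**Possible size, under assumptions.** None of the following inputs is in the protocol. Exponential survival with median 20 or 30 months; censoring uniform on 6 to 60 months; planned sessions uniform on 1 to 3 or 1 to 6; gap between sessions 1.5 or 3 months; lognormal dose per session (SD 0.3); dose without any effect on survival; n = 3,000 per scenario. Then

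sessions given = min(planned, 1 + floor(survival time / gap)).

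With 3 planned sessions and a 3-month gap, a patient who dies at 4 months receives min(3, 1 + 1) = 2, and one who lives 10 months receives min(3, 1 + 3) = 3. Dose thus tracks survival without affecting it.

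| Predictor | C-index |
|---|---|
| Planned sessions alone | 0.49 to 0.52 |
| First-session dose alone | 0.49 to 0.52 |
| Cumulative delivered dose alone | 0.54 to 0.68 |
| Increment of cumulative dose over a clinical model with C of about 0.68 to 0.74 | 0.004 to 0.052 |

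The last row uses one prognostic covariate in a log-linear Cox model over 16 scenarios; in 12 of them the increment was 0.03 or less. The ends of these ranges shift slightly with the random draw. The last row is the relevant one, because the protocol's comparison is against a clinical model and not against chance (0.50).

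**The case against.** The strongest reply is that a conditional generator takes whatever regimen the user enters. The protocol intends regimens to be compared that way, both before treatment and in its counterfactual analysis. On this view the claim about pre-treatment images only contrasts them with follow-up images and does not deny that a regimen must be specified. This stands. A reader might infer that the tool cannot be used as claimed, and that does not follow. What remains is that performance estimated on recorded delivered doses would not describe use with a planned dose.

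Three other strong readings are also unsupported:

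- That DSA and surgical records feed the virtual image. The generator's images are CT/MRI; DSA belongs to the prognosis model and surgical records to a secondary objective.
- That the clinical-only model lacks treatment information. This is possible but not stated, since treatment plan is listed as a clinical feature.
- That the excess of the stand-alone C-index of cumulative dose over 0.50 is the size of the leak. It assumes a cumulative dose, which the protocol does not state, and it is not an increment over a clinical model. It also ignores that dose reaches the survival model only through features of a generated image.

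It can also be said that a variable list belongs in an analysis plan, which is not at hand. That is fair for the full list. But the protocol itself names inputs that sit badly with its own moment of use, and the conflict should be resolved where it arises.

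**Conclusion.** The point holds as an unresolved inconsistency and a leakage risk, not as a demonstrated bias. Followed as written on retrospective charts, the plan allows inputs from after time zero into the models, and it leaves the key comparison unable to credit a gain to the image.

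The size cannot be derived from the documents. If only first-session dose is used, there is no survival-time leakage under the assumptions above, although that dose, if delivered, is still unknown when the regimen is chosen. If cumulative dose is used, the increment depends on the assumed number and spacing of sessions and may be small. The conclusion about the comparator rests on clinical variables being undefined, and the conclusion about DSA on its being taken in the TACE session. The sponsor should settle this before model building.

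**What to change.** - Set the prediction time at the start of treatment, before the first TACE, and state it in the protocol.
- Restrict the primary model's inputs to items dated before that time: CT/MRI, baseline clinical data and the planned regimen category. State for each input whether it is known by then.
- Give all three compared models the same treatment variables, so that the virtual-image model and the clinical-only model differ only by the image.
- Report any model that uses delivered embolic dose, intra-procedural DSA or procedure records as a separate secondary model with a later time zero.

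This proposes no dose or treatment rule. The cost is a date filter, for which dosing dates are already to be collected, and one extra secondary model. The reported performance may be lower.
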